2.1.3.5.2 Intra-operative anastomosis patency

For each anastomosis, Dendrite form R or Castor Anastomosis Data Form asks the question 'Success of anastomosis'. If the response is 'Patent' then intraoperative patency = Yes.

If response = 'failed' or 're-done' then intraoperative patency = No.

Note, this endpoint will only be assessed using the index operation where the timing of anastomosis = 'First attempt'.

The unit of analysis is the anastomosis.

2.1.4 Questionnaires

For each patient, the surgeon will complete two questionnaires:

The exoscope/Symani questionnaire – this comprises 19 questions with a 5 point Likert scale response (Strongly disagree, disagree, neither agree nor disagree, agree and strongly agree), 5 questions with a binary response (yes/no) and 2 questions with a 5 point response (awful, negative, neutral, positive, fantastic).

In this questionnaire, all questions are phrased so that agree and strongly agree represent positive responses, as does 'positive' and 'fantastic'. In addition, for the binary responses all questions except 1, a 'yes' is a positive response. For the question "I needed to switch from robotic suturing to manual suturing because I was not comfortable with 3D vision", a 'No' is a positive response.

All questions will be classified accordingly as positive 'yes' or 'no'. The total number (and percentage) of positive responses will be derived.

If a question is not answered it will not be classified.

The usability questionnaire – this comprises 7 questions using a 5 point Likert scale (from strongly disagree to strong agree), one binary response question (yes/no), one question assessed on a scale of 1-10 and one question with 3 options (this question is used for the key secondary endpoint).

As above, all 5 point Likert scale questions 'agree' and strongly agree' represent a positive response.

Sponsor: MMI Product: Symani system for microsurgical anastomosis Study: PRIMO	
Statistical Analysis Plan Final 22 November 2024	

For the binary response question 'yes' is a positive response and for the scale of 1-10, a high number is a positive response. For classification of positive (yes/no) a value of ≥ 6 will be classified as positive.

For the 3 option question (the primary endpoint), responses of 'complete procedural success' and 'partial procedural success' will be classified as positive.

As for the exoscope questionnaire, the number (and percentage) of positive responses will be derived.

In addition, for each patient, the circulating nurse will complete a questionnaire with 6 questions on a 5 point Likert scale, one question on a 1-10 scale and the same question (as for the surgeon) rating the overall performance with 3 options.

As above, each question will be classified as positive (yes/no) and the number and percentage of positive responses derived.

The scrubbed nurse/sterile assistant will also complete a questionnaire with 5 questions on a 5 point Likert scale, one question on a 1-10 scale and the same question (as for the surgeon) rating the overall performance with 3 options.

As for the circulating nurse, the number (and percentage) of positive responses will be derived.

2.1.5 Safety endpoints

All adverse events (AE, SAE/ADE/SADE/ADE/DD) reported by patients or evaluated by the Surgeon from day 0 to either 30 days after surgery for free flaps, replantation and other procedures, or 24 weeks after surgery for the LVA procedures will be recorded.

All adverse events will be recorded on an adverse event form in the CRF (form U2 in Dendrite or Repeating Data: Adverse Events in Castor). Adverse events will be coded using MedDRA to obtain system organ class (SOC) and preferred term (PT).

All events are assessed by the surgeon for severity (mild/moderate/severe) and seriousness (serious/not serious). In addition, for each event, the surgeon will answer three questions regarding relationship to the device:

- Related to the device
- Related to device malfunction
- Related to device misuse

For each of these assessments, the response is on a 5 point 'scale', namely:

- Not related
- Unlikely
- Possible
- Probable

Sponsor: MMI Product: Symani system for microsurgical anastomosis Study: PRIMO	
Statistical Analysis Plan Final 22 November 2024	

- Definite OR
- Unassessable

They are also asked to note whether there was a different (not device related) cause.

Treatment initiated (if any) and outcome (resolved, resolved with sequelae, ongoing or death) are also recorded.

Event details are recorded as verbatim text.

A separate form will be completed for each event.

Adverse events of special interest, namely, the AEs cited in the literature (e.g., arterial insufficiency, venous congestion) will be flagged based on MedDRA coding.

No further derivations of adverse events data will be undertaken.

2.1.5.1 Additional safety endpoints not defined in the protocol.

2.1.5.1.1 Freedom from device related serious adverse events prior to discharge.

Dendrite's Form U2, and Castor's Repeating Data Form: Adverse Events, is used to collect adverse event data. If there are any adverse events marked as serious where ANY device related question (see note below) is 'possible', 'probable' or 'definite' the event will be classified as a device related SAE = yes.

If ALL AE forms have full responses to the required questions and the AE is not classified as 'device related SAE'=yes then the patient will be classified as device related SAE=No.

If there is a device related SAE but the onset date is after the date of discharge, and the patient has no other event to classify them as having a device related SAE prior to discharge, then they will be classified as free from device related SAE prior to discharge = yes. Otherwise, if there is a SAE that is define as device relates SAE = Yes, then the patient will be classified as free from device related SAE prior to discharge = No.

If it is not possible to classify the event, the patient's classification will be missing. A supporting analysis will use freedom for device related SAE prior to discharge = No for all unclassified patients.

2.1.5.1.2 Freedom from device related adverse events prior to discharge

As described above for freedom from device related SAEs, but any AE which is classified as device related in the intra-operative period would see the patient classified as free from device related adverse events=No.

Sponsor: MMI Product: Symani system for microsurgical anastomosis Study: PRIMO	
Statistical Analysis Plan Final 22 November 2024	

2.1.5.1.3 All cause re-admission rates

Dendrite's Form U1, and Castor's Visit Forms (1-4), is used to collect follow-up information. If all forms have the response to the question 'Any unplanned re-admission'=No, then the patient will be classified as any re-admission within 30 days = no.

If any form has the response to the question 'Any unplanned re-admission to hospital' = Yes, the patient will be classified as 'yes' to any re-admission.

For each form reporting a re-admission, the time to re-admission (in days) will be derived as

Date of re-admission – date of index operation +1.

If there are multiple forms for the same patient where any re-admission = Yes, the time of the earliest re-admission will be used to determine the time to re-admission.

For patients with no re-admissions, time to re-admission will be determined as follows:

In Dendrite, date of follow-up is recorded on form U1 (a follow-up visit form), form U2 (the adverse event form, here it can be recorded twice, once for an AE and once for an adverse device effect) and on form U3 (protocol deviation form).

In Castor, data of follow-up is recorded on Visit Forms (1-4), Repeating Data: Adverse Events, and on Repeating Data: Protocol Deviation Form.

All forms (there may be multiple of each type of form) will be inspected. The latest date will be used to determine time to re-admission.

Time to re-admission (in days) will be calculated as latest follow-up date – date of index operation +1. The patient will be censored in analysis.

2.1.5.1.4 All cause re-operation rates up to 30 days.

Dendrite's Form H, and Castor's Free Flap Operation Visit: Operation Data Form, collects information on whether a donor site re-operation was required, and if so, the data and type of re-operation. In Dendrite, forms J, K, L, M, N and P ask whether a recipient site re-operation was needed (each form collects data for a different recipient site). Form Q collects information on the date and type of recipient site re-operation. In Castor, the repeating data forms: Breast, Head & Neck, Lower Limb, Perineum, Trunk, and Upper Limb Recipient Data ask whether a recipient site re-operation was needed (each form collects data for a different recipient site). The last two questions on each repeating data form for the recipient site collect information on the date and type of recipient site re-operation.

In Dendrite, if all relevant forms (i.e H and the relevant form out of J, K, L, M, N and P) indicate 'no' to re-operation, then the anastomosis will be classified as 'no' for the variable 'any re-operation'. In Castor, if all relevant forms (i.e Free Flap Operation Visit: Operation Data Form and the relevant form out of the repeating data forms: Breast, Head & Neck, Lower Limb, Perineum, Trunk, and Upper Limb Recipient Data) indicate 'no' to re-operation, then the anastomosis will be classified as 'no' for the variable 'any re-operation'.

Sponsor: MMI Product: Symani system for microsurgical anastomosis Study: PRIMO	
Statistical Analysis Plan Final 22 November 2024	

Otherwise, if ANY of the forms indicate 'yes' to 'any re-operations' then the patient will be classified as any re-operation=Yes.

For both donor site re-operations and recipient site re-operations, the time to re-operation (in days) will be derived as

Date of re-operation – date of index operation +1.

If there are multiple anastomosis operations forms for one operation where any re-operation = Yes, the time of the earliest re-operation will be used as the time to re-operation.

If there are no re-operations recorded, the time to re-operation will be determined as follows:

In Dendrite, date of follow-up is recorded on form U1 (a follow-up visit form), form U2 (the adverse event form, here it can be recorded twice, once for an AE and once for an adverse device effect) and on form U3 (protocol deviation form).

In Castor, data of follow-up is recorded on Visit Forms (1-4), Repeating Data: Adverse Events, and on Repeating Data: Protocol Deviation Form.

All forms (there may be multiple of each type of form) will be inspected. The latest date will be used to determine time to re-admission.

Time to re-operation (in days) will be calculated as latest follow-up date – date of index operation +1. The patient will be censored in analysis.

2.1.5.1.5 All cause mortality rates up to 30 days.

Dendrite's Form U1, and Castor's Visit Forms (1-4), is used to collect follow-up information. The patient status at discharge is asked. If the response is 'dead' then the date of death is collected.

Dendrite's Form U2, the adverse event form, and Castor's Repeating Data: Adverse Events, also asks the status at discharge and the date of death (if status is dead). Consistency between forms will be assessed.

For any form where the patient is noted to be dead, the time (in days) to death (i.e. survival time) will be calculated as:

Date of death – date of index operation +1.

For patients who do not have a date of death, survival time will be calculated as follows:

In Dendrite, date of follow-up is recorded on form U1 (a follow-up visit form), form U2 (the adverse event form, here it can be recorded twice, once for an AE and once for an adverse device effect) and on form U3 (protocol deviation form).

In Castor, data of follow-up is recorded on Visit Forms (1-4), Repeating Data: Adverse Events, and on Repeating Data: Protocol Deviation Form.

All forms (there may be multiple of each type of form) will be inspected. The latest date will be used to determine survival time.

Survival (in days) will be calculated as latest follow-up date – date of index operation +1. The patient will be censored in analysis.

Sponsor: MMI Product: Symani system for microsurgical anastomosis Study: PRIMO	
Statistical Analysis Plan Final 22 November 2024	

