2.4.6.2.3 Re-admission within 30 days

As per section 2.1.4.1.3, each patient in the SAS will be assigned to 'Yes' or 'No' for re-admission and the time to re-admission derived.

Patients classified as re-admission = "Yes" will be classified as events, and other patients will be censored. A Kaplan Meier plot will be produced for time to re-admission, overall, by subpopulation (prospective/retrospective) and by procedure type (flap, replantation, lymphatic). From the Product Limit Estimator (PL estimator), an estimate of re-admission rate within 30 days will be obtained.

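### The 30-day re-admission, re-operation and mortality rates censor event-free patients at form dates that need not reflect any assessment of the endpoint, which can lower the rates

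*SAP*

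**What the plan says.** SAP section 2.1.5.1.3 takes re-admission from the visit forms: "Dendrite's Form U1, and Castor's Visit Forms (1-4), is used to collect follow-up information". If every such form says no, the patient is classified as not re-admitted within 30 days. No form at or near day 30 is required.

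The censoring date for event-free patients comes from a wider set of forms. In Dendrite these are U1 (visits), U2 (adverse events) and U3 (protocol deviations). For the other database the section says: "In Castor, data of follow-up is recorded on Visit Forms (1-4), Repeating Data: Adverse Events, and on Repeating Data: Protocol Deviation Form". All of these are inspected, and "The latest date will be used to determine time to re-admission". The patient then enters the analysis as censored: "The patient will be censored in analysis".

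Section 2.1.5.1.4 repeats the rule for re-operation ("Time to re-operation (in days) will be calculated as latest follow-up date" minus the index date, plus one). Its preceding sentence still refers to re-admission. Section 2.1.5.1.5 does the same for death: "The latest date will be used to determine survival time".

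Sections 2.4.6.2.3 to 2.4.6.2.5 read the 30-day figure from the product-limit curve; for re-admission, "an estimate of re-admission rate within 30 days will be obtained". Section 2.4.6.2.4 sets the re-operation rate beside a national flap registry figure of 10.7% (95% limits 9.8% to 11.7%).

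**The concern.** A censoring time should be the last time at which the patient was known to be free of the event. Kaplan-Meier is useful here because it removes a patient from the risk set once follow-up stops. A date from a form that does not record the endpoint keeps the patient in the risk set over days when an event had little or no chance of being captured. The denominator is then too large and the rate too low.

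The visit schedule leaves room for this. Section 2.1.3.2.4 lists visits at 24 hours, day 4 and day 14, then at day 30 for free flaps and replantations or 24 weeks for lymphatic surgery. A patient without the final visit was last due for assessment at day 14. Section 2.5.5 accepts that retrospective patients may have no data at 30 days.

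At stake are three safety rates for a device. For one of them, re-operation, the reader is invited to judge consistency with an outside figure.

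**Working it through.** **Which form records what, and which form supplies the date**

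| Endpoint | Where the SAP says it is recorded | Forms that can set the censoring date |
|---|---|---|
| Re-admission | U1 / Visit Forms 1-4 | visit, adverse event, deviation |
| Re-operation | operation and recipient-site forms | visit, adverse event, deviation |
| Death | U1 / Visit Forms 1-4 and adverse event form | visit, adverse event, deviation |

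The two columns do not match for any endpoint. The gap is smallest for death, where only the deviation form lies outside the recording forms.

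**Does another rule prevent it?** Section 2.5.2 excludes patients whose outcome cannot be determined, but this derivation always yields a censoring time, so the exclusion is not clearly triggered. By contrast, the 30-day flap viability endpoint (section 2.1.3.5.1) rests on a recorded status. For patients who left the study for reasons other than death, that status must date from day 20 or later.

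**Size.** The SAP gives no planned figure for these rates, so there is nothing to reproduce. Inputs:
- R, the true 30-day rate. 10.7% is borrowed from section 2.4.6.2.4 as an illustration.
- s, the share of 30-day events after the last assessment, taken as day 14. Assumed.
- f, the share of patients last assessed at day 14 who carry a later form dated day 30 or after. Assumed.

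Affected patients are taken to have the same risk as the others, and their events after day 14 to go unrecorded.

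Survival to day 14 is S = 1 - R(1 - s). The conditional risk from day 14 to day 30 is h = R×s / S.
- Censoring at the last assessment: 1 - S(1 - h) = R.
- Censoring at the latest form date: 1 - S(1 - h(1 - f)) = R(1 - s×f).

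For R = 0.107, s = 0.3, f = 0.2: S = 1 - 0.107 × 0.7 = 0.9251, and h = 0.0321 / 0.9251 = 0.0347. The first rule gives 10.7%. The second gives 0.107 × (1 - 0.06) = 0.1006, or 10.1%.

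Reported rate when the true rate is 10.7%:

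| s | f = 5% | f = 10% | f = 20% | f = 40% |
|---|---|---|---|---|
| 0.1 | 10.65% | 10.59% | 10.49% | 10.27% |
| 0.3 | 10.54% | 10.38% | 10.06% | 9.42% |
| 0.5 | 10.43% | 10.17% | 9.63% | 8.56% |

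For a rarer event with R = 2%, the same grid runs from 1.99% to 1.60%.

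A simulation of 3,000 trials of 402 patients (s = 0.3, f = 20%) gave means of 10.7% and 10.1%, agreeing with the formula. The sampling standard deviation of the 30-day estimate was about 1.6 percentage points.

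**The case against.** The case forms are not in the file. The SAP says only that a follow-up date is recorded on the deviation form. If that date marks a contact with the patient, it may be sound evidence that the patient was alive. The adverse event form asks about status and date of death, so its date is valid for survival. Mortality is therefore the weakest part of the point. The adverse event form also records treatment and outcome, which might mention a re-operation or re-admission, although the SAP does not use it for those endpoints.

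A reader might infer that missed visits are logged as deviations, that these forms then stand in for the missed assessment, and that all three rates are certainly biased downward. The documents do not support that. They do not say what triggers a deviation form, what it asks, or which day its date represents. The rule has no effect when the last real assessment is at day 30 or later, when no later form exists, or when no event was missed in between. The supportable statement is downward or nil.

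Re-operation raises a further difficulty. Its events come from operation and recipient-site forms that are not tied to visits, so some late events would be captured anyway. Censoring only event-free patients at an earlier visit could then push the estimate slightly upward. Nor can one simply censor at the last form carrying the re-operation question, because those forms are not listed as holding a follow-up date.

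Finally, these are additional endpoints outside the protocol, with no test or decision rule attached, and the SAP undertakes to show the amount of missing data (sections 2.4.1 and 2.5.6). That limits the consequences. It does not supply a reason to take re-admission or re-operation follow-up from a form not described as recording either.

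**Conclusion.** The point holds as a defect in the stated censoring rule: it can count unassessed days as event-free, and no other provision clearly stops it. It applies to re-admission and re-operation, and more weakly to mortality. Where it acts, it multiplies the 30-day rate by (1 - s×f).

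The likely effect is modest: 0.6 percentage points in the central example, which is less than half the sampling standard deviation. At s = 0.5 and f = 20% the reported 9.6% would fall below the registry's lower limit of 9.8% although the true rate equalled the registry's 10.7%, so a descriptive comparison could be affected. All of these sizes rest on assumed s and f, and on the events in question going unrecorded.

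**What to change.** - **Sections 2.1.5.1.3 and 2.1.5.1.4:** remove the protocol deviation and adverse event forms as censoring sources. Censor event-free patients at the last visit form (U1 or Visits 1-4) on which the relevant question was answered. For re-admission this is the re-admission question. For re-operation it is the visit-form question on post-operative need to redo, described in section 2.1.3.2.4.
- **Section 2.1.5.1.4:** correct the sentence that still refers to time to re-admission.
- **Section 2.1.5.1.5:** censor survival at the last visit or adverse event form showing the patient alive. Use a deviation-form date only if it documents contact with the patient.
- **Reporting:** for each endpoint, give the number of patients with an assessment near day 30, overall and by prospective or retrospective source.
- **Sensitivity analysis:** keep the present latest-date rule, because re-operations recorded outside visits could make the earlier censoring slightly informative.

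This is a small wording and programming change that uses data already planned. Some patients will be censored earlier, so the 30-day confidence limits will be slightly wider.

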2.1.5.1.6 Length of hospital stay

The length of hospital stay (in days) will be calculated as :

Date of discharge – date of index operation +1.

If the patient does not have a date of discharge but has a date of death, the date of death will be used as the end date.

Otherwise the result will be missing.

Sponsor: MMI Product: Symani system for microsurgical anastomosis Study: PRIMO	
Statistical Analysis Plan Final 22 November 2024	

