2.1.3 Effectiveness endpoints

Data collected from the operation(s) undertaken during the study will be used to define the effectiveness outcomes. As the timing of operations is important to assess the outcomes, the flow described in figure 2 will be used to assess the timing of procedures.

During the initial hospital stay, patients may undergo multiple operations as per standard of care. The date, start time, and end time of each operation will be recorded (Dendrite: form D, or Castor: Operation Form within procedure specific visit) and these will be used to sort the operations from earliest (index procedure) to latest. The date of discharge from hospital is recorded on Dendrite's form U1, or on Castor's Visit Forms (1-4). The time from the date of the index procedure to the date of discharge (inclusive) is defined as the perioperative period. Any operations recorded after the discharge date will be classified as a re-operation (after hospital re-admission).

Total hospital time (days) = peri-operative time = date of discharge – date of index procedure +1 (days).

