2.4.6.2.6 Length of hospital stay

As per section 2.1.5.1.6 the length of hospital stay (in days) for each patient in the SAS will be derived. Results will be summarized using descriptive statistics for the SAS overall, by subpopulation (prospective/retrospective) and by procedure type (flap, replantation, lymphatic).

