2.5.2 Handling of Dropouts or missing data

For all outcomes, if there is insufficient information available to determine the outcome (including for the continuous measure of length of hospital stay), the patient will be excluded from the analysis in question.

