2.5.5 Windows for time points

All data are expected to be collected within a timeframe of 30 \pm 7 days from the initial study procedure (or 24 weeks \pm 2 weeks for lymphatic surgery). If a patient has a revision procedure where the revision is to a robotic anastomosis, then the timeframe for data collection will be 30-days from the date of the last revision procedure (revision to a robotic anastomosis), where the date of re-operation is prior to the date of discharge. However, for the retrospective data collection, available data will be used whenever possible. Data may not be available at 30 days post-operation.

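### Length of hospital stay excludes any patient still in hospital at the last follow-up form, so the reported mean, SD and maximum may be too low

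*SAP*

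**What the plan says.** SAP 2.1.5.1.6 defines stay in days as "Date of discharge – date of index operation +1". There are two fallbacks. If no discharge date exists but the patient "has a date of death, the date of death will be used as the end date". If neither date exists, "Otherwise the result will be missing".

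SAP 2.5.2 makes the consequence explicit. Where an outcome cannot be determined, "including for the continuous measure of length of hospital stay), the patient will be excluded from the analysis in question".

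SAP 2.4.6.2.6 plans no time-to-event analysis: "Results will be summarized using descriptive statistics for the SAS overall", and also by subpopulation and procedure type.

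Two other sections settle who can have a discharge date:

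- SAP 2.1.3: "The date of discharge from hospital is recorded on" Dendrite form U1 or Castor visit forms 1 to 4. The same section defines total hospital time by the same subtraction, without the death fallback.
- SAP 2.5.5: "All data are expected to be collected within a timeframe of 30" ± 7 days of the initial procedure, or 24 ± 2 weeks for lymphatic surgery. The window is longer after certain revisions made before discharge. The section also warns that 30-day data may be unavailable for retrospective patients.

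By contrast, SAP 2.1.5.1.3 to 2.1.5.1.5 censor re-admission, re-operation and survival at the latest follow-up date, and 2.4.6.2.3 to 2.4.6.2.5 analyse them by Kaplan-Meier.

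**The concern.** A flap or replantation patient who is still an inpatient when the last visit form is completed has no discharge date and no death date. The rule turns that into a missing value and removes the patient. The reason for removal is the outcome itself, a stay longer than follow-up, so the missingness is informative. Whenever such patients exist, the mean is pulled down, and the SD and maximum lose their upper end. Long stays would usually reflect complicated courses, which a safety summary should show.

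The missing category also mixes two different situations. One patient is known to be still in hospital; another went home on a date nobody entered. The missing-data count promised in SAP 2.4.1 does not separate them. SAP 2.5.6 expects a fair amount of missing retrospective data, so a few informative cases could go unnoticed within that count.

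Deaths are folded into the same summary as live discharges. A reader of the table cannot tell how many stays ended in death.

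**Working it through.** The documents give no expected stay, SD, benchmark or share of patients still in hospital, so there is no plan figure to reproduce. The check applies the rules to each type of patient and then illustrates scale under stated assumptions.

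**Step 1: the rules applied by patient type**

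| Patient | Value under 2.1.5.1.6 | Effect on the mean |
|---|---|---|
| Discharged, date recorded | Actual stay | None |
| Died in hospital | Time to death | Up or down, by timing |
| Still in hospital at last form | Missing, excluded | Down |
| Discharged, date unrecorded, alive | Missing, excluded | No fixed direction |
| Discharged, date unrecorded, died later | Time to death | Too long for that patient |

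Only the third row has a certain direction, provided the known stays average less than the excluded ones.

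**Step 2: patients still in hospital**

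Assume known stays average 8 days and a fraction f of patients are still in hospital on day 30. By the SAP's count, which adds 1, each of them has stayed at least 31 days. The reported mean is 8.00. A lower bound for the full mean is (1 − f) × 8 + f × 31 = 8 + 23f.

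- f = 0.5%: 8 + 0.115 = 8.115
- f = 1%: 8 + 0.23 = 8.23
- f = 2%: 8 + 0.46 = 8.46
- f = 5%: 8 + 1.15 = 9.15

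With f = 0 there is no effect.

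**Step 3: the same question with an assumed distribution**

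Simulated lognormal stays, rounded up to whole days, with every stay beyond day 30 dropped:

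| Assumed median, log-SD | Dropped | Mean, all | Mean, after exclusion | Sample median, all → after |
|---|---|---|---|---|
| 7, 0.6 | 0.8% | 8.88 | 8.66 | 8 → 7 |
| 7, 0.8 | 3.5% | 10.15 | 8.95 | 8 → 7 |
| 10, 0.8 | 8.5% | 14.27 | 11.28 | 10 → 10 |
| 14, 0.8 | 17.0% | 19.78 | 13.53 | 15 → 12 |

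The result depends almost entirely on how long the assumed upper tail is, and the documents do not inform that.

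**Step 4: dates missing for record reasons**

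With median 7 and log-SD 0.8, deleting 10% of values completely at random leaves the mean at 10.15 against 10.15. This kind of missingness need not bias the summary.

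**Step 5: deaths**

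Assume 1% of patients die on day t and survivors average 8 days. The mean is 0.99 × 8 + 0.01 × t = 7.92 + 0.01t.

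- t = 3: 7.95
- t = 8: 8.00
- t = 20: 8.12

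The direction depends on when deaths occur.

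**The case against.** Three stronger readings are tempting, and the documents support none of them.

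- **That the longest stays are in fact removed and reported stay is too short.** This is true only if some patients are inpatients at their last form. No count is given, and it may be zero. For lymphatic surgery, with 24 weeks of follow-up, the case is remote. The SAP's own expected source of missing data is retrospective records, where an absent date may only be unrecorded.
- **That counting death as an end of stay makes the stay look short.** The rule removes nobody, and death does end hospital occupancy. Step 5 shows no fixed direction. The rule is not restricted to in-hospital deaths, so a later death with an unrecorded discharge would lengthen the stay. Deaths are also reported on their own in 2.4.6.2.5.
- **That stays are cut off at day 37 for flaps and replantations.** SAP 2.5.5 extends collection after some revisions and uses whatever retrospective data are available. Whether a discharge date can be entered after visit 4 depends on case report forms that are not among the documents.

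Two further objections have force. This is an additional endpoint not defined in the protocol, with no test, benchmark or decision rule; the exclusion is prespecified and the median is reported alongside the mean. In addition, the SAP describes no field that confirms a patient is still in hospital. Without one, censoring every patient who lacks a discharge date would overstate stay for those already at home.

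These objections limit the size and certainty of the effect and narrow the remedy. They do not justify excluding a patient known to be still in hospital when the SAP censors its neighbouring time endpoints.

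**Conclusion.** The point holds as a minor improvement. The rule gives a downward-biased mean, SD and maximum whenever a patient is still in hospital at last follow-up, and the planned missing-data counts would not reveal it. The size cannot be established from the documents: the share of such patients and the distribution of stay in the working are assumptions, and the effect ranges from nothing upwards. Unrecorded dates and deaths do not add to the claim that stay is understated. They are reasons to report each group separately. No conclusion on the primary endpoint depends on this.

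**What to change.** Amend SAP 2.1.5.1.6 and 2.4.6.2.6 as follows, and align 2.5.2.

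1. Censor patients confirmed, by form or data query, to be in hospital at last follow-up at that date, in line with the SAP's other time endpoints.
2. Keep patients whose discharge date is simply unrecorded as missing, and show their number separately. Do not censor them at a follow-up visit.
3. Report time to live discharge: the median with 95% limits and the proportion still in hospital at day 30, overall and by subpopulation and procedure type.
4. Treat in-hospital death as a competing event, or show those patients separately. Do not count it as a discharge.
5. Keep the present descriptive table as secondary.

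The cost is some SAP wording, one extra table, and a query of hospital status for each patient without a discharge date. That query may be slow for retrospective records; patients it cannot resolve stay in the unrecorded group.
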